#### 2.2 Methods

#### 2.2.1 Design

This multi-national and multi-centred mixed-methods study includes two parts:

- I) preliminary studies on usability and analysis of the prototype from technological, educational and behavioural perspective (taxonomy-guided)
- II) the use of a pre-experimental design. USECARE AAL is characterized by an existing complex intervention as well as funding for field-testing SENACA with a relatively small number of participants in three countries. Given the existing resources and limited timeframe of the project, there will be hardly any control over the sample formation as the USECARE AAL participants can neither be chosen by chance nor will they be representative of a certain population. However, the SENACA field-test is considered an opportunity for exploratory purposes on technology acceptance and various outcomes of the prototype. It is considered a cost-effective way to discern whether the potential exploratory findings are worthy of further investigation under more carefully controlled circumstances (Marguis, Larivée, Saey, Dubois & Tousignant, 2015). Thus, a pre-experimental design with a one-group pre-test post-test approach using a repeated post-test has been considered adequate for the exploratory purposes of USECARE AAL (Creswell, 2009; Campbell & Stanley, 1963; Shadish, Cook & Campbell, 2002). This design makes it possible to observe a number of parameters over time using repeated measures and mixed methods (QUAN-qual) during the implementation of the enhanced SENACA prototype (Figure 1). This appears to be the way forward when researching in natural situations where there is a low level of control over context factors and the formation of sample, which both could affect the outcome. While being a reasonable research design for the USECARE AAL purpose, there will be clear limitations because of the pre-experimental character, i.e. that the internal and external validity is low, hypothesis testing is not possible and generalizing results should be avoided.

<sup>5 The QUAN-qual model stands for an explanatory mixed methods design where quantitative data are collected first and are more heavily weighted (41).

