#### 2.2.8 Data analysis

Explorative and descriptive data analyses will mainly be performed in this field-test study with a relatively small sample size.

First, descriptive analysis on usability will give a general overview of how users, both informal carers and patients, view SENACA before having used it. The findings will be compared with perceived usability after having experienced it for the whole intervention period (up to day 100). This will provide insights on practical implications on the design and introduction of SENACA. A qualitative analysis on break-offs and non-response further completes the findings by exploring the barriers and drivers of usage. In addition to that, the usage of the several components of SENACA will be compared regarding frequency and intensity to explore which aspects are more or less accepted by the user groups.

In a second step, the clinical and behavioural parameters and quality of life will be screened at baseline measurement. This initial description gives further insights into the characteristics of the sample. Changes in parameters over time will be explored to gain insight into the functionality of SENACA.

Overall, mean values will be compared on the basis of non-parametric tests to identify significant differences between groups. Even though the study does not meet the requirements of an experimental design, the ex-ante and ex post measurement allows monitoring changes of the observed variables. Bias due to non-observable errors may be possible.

Data from qualitative study parts (i.e. interview transcripts, content from open-ended questions or user forums) will be coded applying thematic analysis (Bradley, Curry & Devers, 2007) in order to categorize the data as well as to identify patterns leading to a nuanced evaluation of the usability of SENACA from a technological, educational and behaviour perspective. The qualitative analysis will be guided by taxonomies and frameworks on the subject of matter to be used as sensitizing concepts, for instance Michie et al. (2013) or Greenhalgh et al.(2015). Computer-aided qualitative data analysis (most likely MaxQDA®) will be used for coding and synthesising the findings.

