#### 2.2.9 Limitations

A longitudinal approach is used in this study to examine changes over time and to identify the usability as well as adherence of participants with the programme as indicators of its usefulness in everyday life. However, the adopted design and study procedures will lack the sufficient statistical power to detect significant findings and may result in potential bias given the lack of a control group and lack of randomisation in recruiting participants. Therefore, the analysis is primarily descriptive and will be used to gain in-depth insight into the user experience with the enhanced SENACA prototype in participating European countries.

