#### 4.2.1 Service description

The service provided by the SENACA platform is intended for persons with one or more chronic diseases, and their caregivers. It consists of a web-based solution with questionnaires, in addition to automatic transfer of monitoring values for e.g. blood pressure and heart rate, blood glucose, lung capacity (SpO2), body weight, and activity (step counts). Which monitoring parameters that will be collected, depends on which chronic disease the patient has. In Norway, the main target group is patients with chronic heart failures and their informal caregivers.

The gathered health data is combined with an a priori individual online assessment of health, as part of a personalized health plan and personal health record. The initial assessment allows personalizing the intervention to individual end-users using pre-defined algorithms based on international classifications and guidelines.

Study participants will use the SENACA prototype at home for a 3-month period (100 days) and visit local healthcare providers three times for standard clinical procedures (laboratory tests). Users will get personalized weekly online feedback on tasks (activity, nutrition, health literacy) as well as "rewards" (gamification). Informal caregivers will get a short introduction/tasks (e-learning) on motivational interviewing.

<sup>12 This risk assessment was conducted in November-December 2015 and January 2016 by [name]. The following key personnel participated in the risk assessment meetings: [name], [name], and [name]. In addition, some clarifications were obtained in e-mail communication with [name], CTO, Medical Network EMN AG, Switzerland.

Figure 3: SENACA start page with login

The center of the structured self-management program is a web site and a complementary smartphone app, both for patients and caregivers. It includes five main elements:

- A personal program that can be accessed by end-users with their own personal computers, notebooks or mobile devices. It collects data like *personal goals*, values from *monitoring devices, medication adherence, nutrition,* and *physical activity*. It also presents relevant *health-related evidence-based knowledge* to the users.

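### Section 2.2.8 plans significance tests of means between groups, but the study has one group measured repeatedly and section 2.2.1 rules out hypothesis testing

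*Protocol*

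**What the plan says.** Section 2.2.1 of the protocol chooses "a pre-experimental design with a one-group pre-test post-test approach using a repeated post-test". It lists the limits of that choice, among them that "hypothesis testing is not possible and generalizing results should be avoided".

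Section 2.1.1 gives the Part II objective: to explore how clinical, behavioural and quality-of-life parameters evolve from baseline to the end of data collection. Table 6 schedules the repeated outcomes at Day 0, Day 50 and Day 100.

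Section 2.2.8 opens cautiously: "Explorative and descriptive data analyses will mainly be performed in this field-test study with a relatively small sample size". It plans to compare usability before use with usability after use, and to explore change over time. It then gives its one inferential rule: "Overall, mean values will be compared on the basis of non-parametric tests to identify significant differences between groups". The sentence after it returns to before-and-after measurement. Section 2.2.8 does not say what the groups are.

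Section 2.2.9 adds that the design and procedures "will lack the sufficient statistical power to detect significant findings" and calls the analysis primarily descriptive.

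**The concern.** Three things do not fit together.

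- **Testing.** Section 2.2.8 requires tests aimed at significance. Section 2.2.1 says that hypothesis testing cannot be done in this design. An analyst cannot follow both.
- **Groups.** A one-group study with repeated measurement has no between-group outcome comparison built into it. The Part II question is about change in the same people.
- **Means.** Standard rank tests do not test equality of means. A rank-sum test concerns whether values in one sample tend to exceed those in the other. A signed-rank test concerns whether differences are symmetric about zero. Either one speaks to means only under added assumptions about shape.

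Within-person change is the main quantitative information this design can give. Section 2.1.1 presents the results as a possible basis for a later study of effectiveness. If the rule is read literally and unpaired tests are run, real change could be missed. If p-values are reported without a stated status, readers cannot tell whether the protocol stands behind them.

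**Working it through.** **No figure to reproduce.** The protocol states no sample size, alpha, correlation, standard deviation or named test. The check is therefore a reading of the possible meanings of groups, plus a sensitivity calculation on assumed inputs.

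**Step 1: what the groups could be.**

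1. *Time points.* The sentences around the rule are about before and after. The samples are then the same people, and the comparison must be paired.
2. *Patients and informal caregivers.* Section 2.2.3 describes two end-user groups and section 2.2.8 speaks of user groups. Under Recruitment in section 2.2.2, a patient and the named caregiver enter together. These are linked pairs, not independent samples.
3. *Countries or diagnoses.* The people differ, so an unpaired test would be formally possible, but case mix may differ. The documents show this for one site: "In Norway, the main target group is patients with chronic heart failures and their informal caregivers" (section 4.2.1). Section 2.2.8 names no country contrast.

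Readings 2 and 3 do not answer the Part II question. Reading 1 does, but only if the analysis is within persons.

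**Step 2: the cost if reading 1 were analysed unpaired.** Assumptions, none from the protocol: equal variance σ² at both times, within-person correlation r, n people, two-sided nominal alpha 0.05.

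- Paired standard error: σ·√(2(1 − r)/n)
- Independent-sample standard error: σ·√(2/n)
- Ratio, independent to paired: 1/√(1 − r)
- True size of the unpaired large-sample test: 2·[1 − Φ(1.96/√(1 − r))]

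| r (assumed) | SE ratio | True size at nominal 5% |
|---|---|---|
| 0.3 | 1/√0.7 = 1.20 | 1.9% |
| 0.5 | 1/√0.5 = 1.41 | 0.56% |
| 0.7 | 1/√0.3 = 1.83 | 0.035% |

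The ratio does not depend on n.

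**Step 3: the same check on rank tests.** In 3,000 simulated bivariate normal data sets per setting with no change and n = 30 (assumed), the unpaired Mann-Whitney test rejected in 1.9%, 0.6% and 0.1% at r = 0.3, 0.5 and 0.7. The signed-rank test rejected in 5.0%, 4.5% and 5.1%. The unpaired test is conservative, and the paired test keeps its level.

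**Step 4: patient-caregiver contrasts.** The same ratio applies, with the within-pair correlation in place of r. If that correlation is positive, the independent-sample standard error is too large; if negative, too small. The protocol gives no value, so this error cannot be sized.

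**The case against.** The strongest reply is that section 2.2.8 fixes very little. It names no test, standard error, interval or alpha, and nowhere says that Day 0, Day 50 and Day 100 will be treated as independent samples. Signed-rank and Friedman tests are also non-parametric. The choice of test may properly sit in a statistical analysis plan that is not shown. Groups may simply mean patients and caregivers. The same section does plan to look at change over time. The protocol also warns repeatedly about bias, low validity and limited power, and section 2.3 says that a controlled trial is needed.

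Most of this stands, and it rules out three stronger readings that a reader might infer.

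- *That the plan yields wrong error bars.* It does not say so. The variance error arises only if repeated or linked observations are analysed as independent.
- *That many false positives will follow.* An unpaired analysis of positively correlated repeated measurements rejects too rarely. A surplus of chance findings would need correctly paired tests, many of them, with no adjustment. The protocol does not state that they are unadjusted. The two risks belong to different readings and cannot be added.
- *That country is tied to diagnosis throughout.* The documents support this for Norway only, and there only as the main target group.

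The reply does not remove the conflict. The words mainly and primarily leave room for some testing, but section 2.2.1 is categorical. A later analysis plan cannot comply with both sections. Nor does the reply supply a meaning of groups that serves Part II, or make rank tests into tests of means. The statement on power in section 2.2.9 is by itself a caveat on tests, not a ban on them; the contradiction lies between sections 2.2.1 and 2.2.8.

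**Conclusion.** The point holds as a moderate inconsistency in the stated analysis. Three parts are on the face of the protocol and need no assumption: tests for significance are planned in a design said not to permit them, the comparison is framed between undefined groups when the objective is change within persons, and rank tests are described as comparing means.

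The numerical part is conditional. If time points were treated as independent groups, the standard error would be about 1.4 times too large at r = 0.5 and 1.8 times at r = 0.7. A change would have to be larger by the same factor to reach significance. This rests on equal variances and on assumed correlations. Treating patients and caregivers as independent would also be wrong, by an amount the documents do not allow one to compute.

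**What to change.** Replace the rule in section 2.2.8 with wording such as:

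> Within-person change from Day 0 to Day 50 and from Day 0 to Day 100 is reported with 95% confidence intervals, separately for patients and caregivers. Mean change is used where suitable, the Hodges-Lehmann estimate with signed-rank interval for ordinal or skewed scales, and paired proportions for categorical items such as smoking. The number contributing and the number lost are given at each time point. Patient-caregiver contrasts are within-pair differences. Contrasts by country or diagnosis are descriptive.

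Then reconcile section 2.2.1 in one of two ways:

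- make no significance claims and leave section 2.2.1 as it is; or
- keep paired p-values, label them exploratory and unadjusted, and amend section 2.2.1.

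Either is coherent. The cost is protocol wording only, with no new data or visits. The downside is that p-values cannot be quoted as confirmatory findings, which the design could not support in any case. Stating the numbers lost matters because attrition is itself a usability parameter in Annex 1, and change among those who remain may not represent everyone who started.

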#### Supplementary analysis

In addition to the previously described analyses of USECARE AAL, in Israel, a supplementary analysis will be performed. The Assuta team will perform the interRAI Community Health Assessment (CHA) with the Israeli participants in order to assess in depth their health conditions, functioning, cognition, mood, pain, continents, mobility, physical and social environment, care needs, as well as health care utilization. The assessment will determine risks and treatable conditions and algorithmically produce care goals to do, as protocols for the formal care givers. This system is highly reliable and valid and in use in the Assuta environment for care of old people. The interRAI system is in use in 40 countries and sometimes demanded by care providers, insurers, and governments (US, Canada, Finland, Belgium, Hong-Kong, New-Zealand and others). This will create a parallel track of formal and informal care to be investigated. USECARE is important way to empower informal caregivers. However it is always additional to the formal care. This structured and well-determined formal care system will produce quality interRAI data, which will be compared to the automated and self-reported measurements from the USECARE AAL study.

#### 2.2.9 Limitations

A longitudinal approach is used in this study to examine changes over time and to identify the usability as well as adherence of participants with the programme as indicators of its usefulness in everyday life. However, the adopted design and study procedures will lack the sufficient statistical power to detect significant findings and may result in potential bias given the lack of a control group and lack of randomisation in recruiting participants. Therefore, the analysis is primarily descriptive and will be used to gain in-depth insight into the user experience with the enhanced SENACA prototype in participating European countries.

#### 2.3 Conclusion

At the end of this study, we expect to have insights on how to further improve a selfmanagement support system for community-dwelling older adults and their informal caregivers that is useful in everyday life and may be related to behaviour change, improved clinical outcomes and quality of life. Further research including a controlled trial is needed to test the effectiveness of the enhanced SENACA prototype. Findings from this study can be used to identify those features of the prototype that should be optimised to inform an on-going improvement of the self-management support system for its scalability in the respective European countries.

#### **3** SENECA web-platform usability tests

#### 3.1 Introduction

USECARE is a 2-year EU financed project (2015-16) with the objective of implementing and testing a self-management tool for people with chronic diseases. Partners in Israel, Norway and Switzerland will host pilot sites, recruit users and see to that the implementation, testing and data gathering go as planned. The objective is to evaluate the use of the self-management system, focusing on the use of the system (usability, user-friendliness, satisfaction) and if parameters connected to QoL and some health parameters stabilize or change during the project period.

During the intervention patients in three countries (Israel, Norway and Switzerland) will be using medical devices to record health related data (different patient groups will be using medical devices according to their symptoms). Bluetooth will transmit the data via a HUB to a database. The patients can then access their personal data on a web-platform. The patients will be able to set target values for the health related parameters, making plans for activities, manage medication, read about the disease and register information in a diary. Every patients are to name an informal caregiver who also will using the web-platform. The aim is to motivate the patients to change behaviour based on relevant information and continuously updated health related information. Informal caregivers will get opportunity to support the patient in her or his effort, based on the same data

Before the study started, we recruited test users in the three pilot countries to evaluate the SENACA system in terms of usability and feasibility of the system. The test users were recruited based on criteria that resembled the ones that are to be used for the recruiting of the patients, except that they are not necessarily patients. The test users were equipped with the same medical devices that the patients are going to use during the intervention.

#### 3.1.1 Usability testing

Usability testing is a technique used to evaluate a product by testing it with users. Usability is defined in terms of aspects, such as time to learn how to use the system, user's errors, time to fulfill a task, user's satisfaction and acceptability, etc.

As Jakob Nielsen points out elaborating usability tests with a lot of users are a waste of resources (Nielsen, 2000). You learn less and less for the extra users you add because there will be overlap in what you saw with the previous users. However, people are different and you find something particular with new users, but after added some extra users you will be observing the same thing repeatedly. Nielsen is claiming that after the fifth users, you do not get much new information. 15 users is enough to identify all the usability problems in a design, but Nielsen is advocating spending resources on 3 studies with 5 users each rather than recruiting 15 users. It is this iterative design approach that allows you to improve the design gradually by letting the users test the redesigned versions of the system.

When users are very different you need to test with additional users. Still he thinks that different groups of users have many things in common, because usability problems are related to the way people interact with a web site (Nielsen, 2000). Nielsen is advocating small numbers of test users, even when we anticipate that there are several highly distinct groups of users. You do not need to include as many users as you need in a test with a single group of users, he

says, and recommends that you recruit 3 users from each group if you are testing three or more groups of users.

Different methods can be applied when doing usability tests. The Hallway technique is a quick and cheap method were you invite people passing in a hallway to use the system. The developers or researchers can observe while the users operate the system. Another technique is to invite test users that have some of the same characteristics as the real users. It is more resource demanding than the Hallway method but potentially we will get more valid information, especially if we anticipate that some background variables will affect their experiences and views. The test users are then invited to do specific tasks while the developers, researcher or another person are observing how they are performing the tasks. The session can be followed up by an interview and/or a questionnaire in order to get a more comprehensive understanding of what the users think about the functional and non-functional (look and feel, performance etc.) aspects of the system. The use of interview is more resource demanding than questionnaire, but by interviewing, we are getting richer information.

A third technique is to let users use the system in their own home environment or at work. Test users are invited based on some variables that are similar to the potential users. The users will be using the system for a longer period and perform specified tasks. We can use different methods to gather information about how the users react to the system and what kind of problems they encounter. The test users can give instant feedback (e-mail, drop box etc.) or they can respond after a period, using interviews (individual or focus group interview) and/or give feedback via a questionnaire (open-ended questions included).

